4.1.2 Primary Efficacy Endpoint

4.1.2.1 The responder rate as identified by the OMERACT-OARSI responder index at 39 weeks post treatment comparing the Cingal group to the triamcinolone hexacetonide group.

The response rate for the Cingal group and Triamcinolone Hexacetonide (TH) group will be calculated and tested using Fisher's exact test. Formally, the hypothesis to be tested is:

$H_0: \pi_C = \pi_T$ versus $H_0: \pi_C \neq \pi_T$

Where π_C is the responder rate for the Cingal group and π_T is the responder rate for the triamcinolone hexacetonide group.

This will be estimated and tested using PROC FREQ with the EXACT option. The results will be displayed similar to:

Summary of the OMERACT-OARSI Responder Rates at 39 Weeks

Parameter	Cingal	Monovisc	TH
Estimate n/N (%)			
Cingal vs TH (Primary) (p-value)			

Parameter	Cingal	Monovisc	TH
Cingal vs Monovisc (p-value)			
Monovisc vs TH (p-value)			

4.1.3 Secondary Efficacy Endpoints

There are multiple secondary endpoints. In order to preserve the integrity of the Type I error, these will be tested in a hierarchical manner. The order of the testing is as the order presented here.

The change from baseline in knee pain as measured by the WOMAC Pain Score (100 mm VAS) at 39 weeks post treatment comparing the Cingal group to the TH group.

This secondary efficacy endpoint is the change from baseline in knee pain as measured by the WOMAC Pain Score (100 mm VAS) at 39 weeks post treatment comparing the Cingal group to the TH group.

Data will be analyzed via an analysis of variance (ANOVA) with a term for treatment and baseline pain score as a covariate. The primary hypothesis will be tested by a predefined contrast for comparing the Cingal group to the triamcinolone hexacetonide group. Formally, the hypothesis to be tested is:

$$H_0: \mu_{DC} = \mu_{DT} \text{ versus } H_A: \mu_{DC} \neq \mu_{DT}.$$

Where μ_{DC} is the mean change from baseline in the WOMAC Pain Score for the Cingal group at 39 weeks and μ_{DT} is the mean change from baseline in the WOMAC Pain Score for the triamcinolone hexacetonide group at 39 weeks. Since there are three treatment groups in this study, this hypothesis will be tested using a one way ANOVA and constructing a contrast for this hypothesis. This process is the same as using a baseline pain adjusted two-sample t-test with the common variance estimate from the ANOVA.

The anticipated SAS code for this analysis is given as:

The mean difference will be estimated and tested using the contrasts from PROC GLM on the responses at the 39 week time period.

```

PROC GLM DATA=EFF;
  WHERE VISITNO = 39;
  CLASS TRT;
  MODEL WOMODIFF = BASEWOM TRT / TYPE3 ALPHA=0.05;
  ESTIMATE 'CINGAL VS MONOVISC' TRT 1 -1 0 ;
  ESTIMATE 'CINGAL VS TH'      TRT 1 0 -1 ;
  ESTIMATE 'MONOVISC VS TH'    TRT 0 1 -1 ;
  LSMEANS TRT / DIFF CL ALPHA=0.05;
  FORMAT TRT TRTF. ;
  RUN;

```

In this model, the WOMODIFF is the difference in WOMAC Pain Scores from baseline. The variable TRT is a categorical variable where 1 = Cingal, 2=Monovisc, and 3=TH. The variable

BASEWOM is the baseline WOAMC scores and the variable VISITNO is the visit number identifier. ODS statements will be used to output the contrasts and the mean differences into data sets that can be easily displayed using PROC REPORT. The primary analysis will be comparing Cingal to TH.

The tables for this analysis will be displayed as:

Summary of Least Squares Means at 39 weeks – WOMAC Pain Score

Treatment Group	Mean Percent Improvement LS Mean	Standard Error
Cingal		
Monovisc		
TH		

Summary of Differences in Mean Responses at 39 Weeks – WOMAC Pain Score

Treatment Group	Mean Percent Improvement	Standard Error	Lower Confidence Limit	Upper Confidence Limit	p-value
Cingal – Monovisc					
Cingal – TH					
Monovisc - TH					

The change from baseline in WOMAC Physical Function score at 39 weeks post treatment comparing the Cingal group to the triamcinolone hexacetonide group.

This secondary efficacy endpoint is the change from baseline in WOMAC Physical Function Score at 39 weeks post treatment comparing the Cingal group to the TH group.

Data will be analyzed via an analysis of variance (ANOVA) with a term for treatment and baseline Physical Function score as a covariate. The hypothesis will be tested by a predefined contrast for comparing the Cingal group to the TH group. Formally, the hypothesis to be tested is:

$$H_0: \mu_{DC} = \mu_{DT} \text{ versus } H_A: \mu_{DC} \neq \mu_{DT}.$$

Where μ_{DC} is the mean change from baseline in the WOMAC Physical Function Score for the Cingal group at 39 weeks and μ_{DT} is the mean change from baseline in the WOMAC Physical Function Score for the TH group at 39 weeks.

The change from baseline in WOMAC Stiffness score at 39 weeks post treatment comparing the Cingal group to the triamcinolone hexacetonide group.

This secondary efficacy endpoint is the change from baseline in WOMAC Stiffness Score at 39 weeks post treatment comparing the Cingal group to the TH group.

Data will be analyzed via an analysis of variance (ANOVA) with a term for treatment and baseline Stiffness score as a covariate. The hypothesis will be tested by a predefined contrast for comparing the Cingal group to the TH group. Formally, the hypothesis to be tested is:

$$H_0: \mu_{DC} = \mu_{DT} \text{ versus } H_A: \mu_{DC} \neq \mu_{DT}.$$

Where μ_{DC} is the mean change from baseline in the WOMAC Stiffness Score for the Cingal group at 39 weeks and μ_{DT} is the mean change from baseline in the WOMAC Stiffness Score for the TH group at 39 weeks.

The change from baseline in Total WOMAC score at 39 weeks post treatment comparing the Cingal group to the triamcinolone hexacetonide group.

This secondary efficacy endpoint is the change from baseline in Total WOMAC Score at 39 weeks post treatment comparing the Cingal group to the TH group.

Data will be analyzed via an analysis of variance (ANOVA) with a term for treatment and baseline Total WOMAC score as a covariate. The hypothesis will be tested by a predefined contrast for comparing the Cingal group to the TH group. Formally, the hypothesis to be tested is:

$H_0: \mu_{DC} = \mu_{DT}$ versus $H_A: \mu_{DC} \neq \mu_{DT}$.

Where μ_{DC} is the mean change from baseline in the Total WOMAC Score for the Cingal group at 39 weeks and μ_{DT} is the mean change from baseline in the Total WOMAC Score for the TH group at 39 weeks.

The change from baseline in the Patient Global Assessment at 39 weeks post treatment comparing the Cingal group to the triamcinolone hexacetonide group.

Since this is a secondary endpoint the data will be analyzed for each time point individually with no adjustment for multiplicity. Data will be analyzed via an analysis of variance with a term for treatment and baseline PGA score as a covariate. The primary hypothesis will be tested by a predefined contrast for comparing the Cingal group to the Triamcinolone Hexacetonide group. Formally, the hypothesis to be tested is:

$H_0: \mu_{DC} = \mu_{DT}$ versus $H_A: \mu_{DC} \neq \mu_{DT}$.

Where μ_{DC} is the mean change from baseline in the Patient Global Assessment Score for the Cingal group and μ_{DT} is the mean change from baseline in the Patient Global Assessment Score for the triamcinolone hexacetonide group. Since there are three treatment groups in this study, this hypothesis will be tested using a one way ANOVA and constructing a contrast for this hypothesis. This process is the same as using a two-sample t-test with the common variance estimate from the ANOVA.

The mean difference will be estimated and tested using the contrasts from PROC GLM on the responses by week with the 39 week time period being the time point of interest for the analysis of this secondary endpoint.

4.1.3.4 The change from baseline in the Evaluator Global Assessment through 39 weeks post treatment comparing the Cingal group to the triamcinolone hexacetonide group.

Since this is a secondary endpoint the data will be analyzed for each time point individually with no adjustments for multiplicity. Data will be analyzed via an analysis of variance with a term for treatment and baseline EGA score as a covariate. The primary hypothesis will be tested by a predefined contrast for comparing the Cingal group to the triamcinolone hexacetonide group. Formally, the hypothesis to be tested is:

$H_0: \mu_{DC} = \mu_{DT}$ versus $H_A: \mu_{DC} \neq \mu_{DT}$

Where μ_{DC} is the mean change from baseline in the Evaluator Global Assessment for the Cingal group at 39 weeks and μ_{DT} is the mean change from baseline in the Evaluator Global Assessment for the triamcinolone hexacetonide group at 39 weeks. Since there are three treatment groups in this study, this hypothesis will be tested using a one way ANOVA and constructing a contrast for this hypothesis. This process of constructing a contrast is the same as using a two-sample t-test with the common variance estimate from the ANOVA.

The usage of rescue medication through 39 weeks post treatment comparing the Cingal group to the triamcinolone hexacetonide group.

This secondary efficacy endpoint is the usage of rescue medications through 39 weeks post treatment comparing the Cingal group to the TH group.

The hypothesis will be tested by a predefined contrast for comparing the Cingal group to the TH group. Formally, the hypothesis to be tested is:

$H_0: \mu_{DC} = \mu_{DT}$ versus $H_A: \mu_{DC} \neq \mu_{DT}$.

Where μ_{DC} is the total usage of rescue medications for the Cingal group at 39 weeks and μ_{DT} is the mean change from baseline in the WOMAC Pain Score for the TH group at 39 weeks.

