Where μ_{DC} is the mean change from baseline in the Patient Global Assessment Score for the Cingal group at 39 weeks and μ_{DT} is the mean change from baseline in the Patient Global Assessment Score for the triamcinolone hexacetonide group. At 39 weeks. Since there are three treatment groups in this study, this hypothesis will be tested using a one way ANOVA and constructing a contrast for this hypothesis. This process is the same as using a two-sample t-test with the common variance estimate

from the ANOVA.

The change from baseline in the Evaluator Global Assessment through 39 weeks post treatment comparing the Cingal group to the triamcinolone hexacetonide group.

Since this is a secondary endpoint the data will be analyzed for each time point individually with no adjustments for multiplicity. Data will be analyzed via an analysis of variance with a term for treatment and baseline pain score as a covariate. The primary hypothesis will be tested by a predefined contrast for comparing the Cingal group to the triamcinolone hexacetonide group. Formally, the hypothesis to be tested is:

$$H_0: \mu_{DC} = \mu_{DT} \text{ versus } H_A: \mu_{DC} \neq \mu_{DT}$$

Where μ_{DC} is the mean change from baseline in the Evaluator Global Assessment for the Cingal group at 39 weeks and μ_{DT} is the mean change from baseline in the Evaluator Global Assessment for the triamcinolone hexacetonide group at 39 weeks. Since there are three treatment groups in this study, this hypothesis will be tested using a one way ANOVA and constructing a contrast for this hypothesis. This process of constructing a contrast is the same as using a two-sample t-test with the common variance estimate from the ANOVA.

The usage of rescue medication through 39 weeks post treatment comparing the Cingal group to the triamcinolone hexacetonide group.

This secondary efficacy endpoint is the usage of rescue medications through 39 weeks post treatment comparing the Cingal group to the TH group.

The hypothesis will be tested by a predefined contrast for comparing the Cingal group to the TH group. Formally, the hypothesis to be tested is:

$$H_0: \mu_{DC} = \mu_{DT} \text{ versus } H_A: \mu_{DC} \neq \mu_{DT}.$$

Where μ_{DC} is the total usage of rescue medications for the Cingal group at 39 weeks and μ_{DT} is the mean change from baseline in the WOMAC Pain Score for the TH group at 39 weeks.

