3.2 SECONDARY EFFICACY ENDPOINTS

- The change from baseline in knee pain as measured by the WOMAC Pain Score (100 mm VAS) at 39 weeks post treatment comparing the Cingal group to the Triamcinolone Hexacetonide (TH) group.
- The change from baseline in WOMAC Physical Function score at 39 weeks post treatment comparing the Cingal group to the TH group.
- The change from baseline in WOMAC Stiffness score at 39 weeks post treatment comparing the Cingal group to the TH group.
- The change from baseline in Total WOMAC score at 39 weeks post treatment comparing the Cingal group to the TH group.
- The change from baseline in the Patient Global Assessment 39 weeks post treatment in the Cingal group compared to the TH group.
- The change from baseline in the Evaluator Global Assessment at 39 weeks post treatment in the Cingal group compared to the TH group.
- The usage of rescue medication through 39 weeks post treatment in the Cingal group compared to the TH group.

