4.2 STATISTICAL METHODS

Tabulation of summary statistics, graphical presentations, and statistical analyses will be performed using SAS® software 9.1.3 or higher version. Where not otherwise specified, the last pre-treatment observation will be used as baseline for calculating post-treatment changes from baseline. The primary presentations and analyses will be based on data pooled across study centers. Relevant summaries for individual centers, or combinations of centers, may be presented for primary data. All testing and confidence intervals will use a significance level of 5%.

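### The hierarchical secondary tests are not made conditional on the primary test and have no stated stopping rule; two wording faults (global assessments, rescue-medication null) need correcting in the same place.

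*SAP*

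**What the plan says.** Both documents open the secondary-endpoint section (Protocol 12.1.2, SAP 4.1.3) by noting that there are several secondary endpoints and adding: "In order to preserve the integrity of the Type I error, these will be tested in a hierarchical manner". The order is the order of presentation: WOMAC pain, physical function, stiffness, total WOMAC, Patient Global Assessment (PGA), Evaluator Global Assessment (EGA), rescue-medication use. Each compares Cingal with TH.

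The primary endpoint sections (Protocol 12.1.1, SAP 4.1.2) specify Fisher's exact test on the week-39 responder rate and do not mention the secondary endpoints. On the level, SAP 4.2 says "All testing and confidence intervals will use a significance level of 5" percent, and Protocol 12.2 says the same.

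Two of the seven endpoints carry a further sentence. For PGA, both documents have "Since this is a secondary endpoint the data will be analyzed for each time point individually with no adjustment for multiplicity"; for EGA, "Since this is a secondary endpoint the data will be analyzed for each time point individually with no adjustments for multiplicity". For PGA the SAP adds that the model is fitted by week, "with the 39 week time period being the time point of interest for the analysis of this secondary endpoint".

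For rescue medication, the Cingal parameter "is the total usage of rescue medications for the Cingal group at 39 weeks", while the TH parameter is defined as the mean change in WOMAC pain. Both documents have this. A predefined contrast is named; no model is.

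**The concern.** A hierarchy protects the error rate only across the tests it links. Here the stated hierarchy links the secondaries to one another and leaves the primary outside. If the responder comparison fails and WOMAC pain gives p<0.05, the documents do not say whether pain may be claimed. Nor do they say in words that testing stops at the first non-significant secondary, although that is the ordinary meaning of testing hierarchically. Two analysts could follow the same plan and produce different lists of allowable claims, and settling the question after unblinding would make the choice depend on the data.

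The PGA and EGA sentences add a smaller doubt. The reason they give for not adjusting is that the endpoint is secondary, whereas the opening paragraph introduces error control because there are multiple secondary endpoints. The rescue null, taken literally, compares two different variables and cannot be tested.

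**Working it through.** **Inputs.** Each test is at 5% (Protocol 12.2, SAP 4.2), two-sided (the alternatives are not-equal). Planned group sizes are 256 Cingal and 64 TH (Protocol 12.1, SAP 4.1.1). The documents give no correlations between endpoints, so 0.5, 0.8 and 0.9 are assumptions. They state no familywise error rate, so there is no plan figure to reproduce.

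**Which tests run freely.** Assume all null hypotheses are true and that the secondary sequence stops at its first failure. The sequence can then yield a false claim only if its first test, WOMAC pain, rejects.

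- Sequence gated on the primary: one free test, so familywise error is 5%.
- Sequence not gated: two free tests, the primary and WOMAC pain.

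**Ungated, independent tests.** 1 − (1 − 0.05)² = 1 − 0.9025 = 9.75%. The bound under any dependence is 0.05 + 0.05 = 10%.

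**Ungated, correlated tests.** For two standard normal statistics with correlation ρ, familywise error is 1 − P(|Z₁| ≤ 1.96 and |Z₂| ≤ 1.96). Numerical integration gives:

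| Assumed ρ | Familywise error |
|---|---|
| 0 | 9.75% |
| 0.5 | 9.07% |
| 0.8 | 7.81% |
| 0.9 | 7.04% |

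A simulation with 1,000,000 draws agreed within 0.1 percentage points.

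**Allowance for Fisher's exact test.** The primary is not an exact 5% test. Enumerating all outcomes for 256 versus 64 with complete data, its true size is 4.5% at a common responder rate of 0.4, 4.2% at 0.5, 4.5% at 0.6, 4.3% at 0.7 and 4.1% at 0.8. The independent figure becomes 1 − (1 − 0.041)(0.95) = 8.9% at the low end and 1 − (1 − 0.045)(0.95) = 9.3% at the high end.

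**PGA and EGA, side by side.** The opening paragraph covers all the secondaries, and PGA and EGA are fifth and sixth in its order. Their own paragraphs then decline to adjust when analysing each time point. Week 39 is one of those time points, and no sentence says that its test keeps its place in the sequence.

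**Rescue null, side by side.** The heading and opening sentence compare rescue use through week 39 between Cingal and TH. The formal hypothesis sets rescue use in Cingal against WOMAC pain change in TH. The first states the intent; the second repeats the parameter definition from the pain endpoint.

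**The case against.** The strongest objection concerns PGA and EGA. A reader might infer that the no-adjustment sentences take both out of the hierarchy. The free tests would then number three if the sequence is gated (1 − 0.95³ = 14.3%) or four if it is not (1 − 0.95⁴ = 18.5%), assuming independence. The documents do not support that reading well:

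- Both endpoints stand in the ordered list.
- The sentence is about analysing time points one by one.
- The SAP singles out week 39 for PGA, and both documents state the EGA hypothesis at 39 weeks.
- Time points not described under the primary or secondary endpoints are already exploratory, with PGA and EGA listed by name (Protocol 7.3 and 12.1.3, SAP 3.3 and 4.1.4).
- A fixed sequence runs each test at full alpha, so making no adjustment does not contradict it.

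This objection stands. What remains is that the text never says the week-39 tests stay in the sequence. The EGA heading, "The change from baseline in the Evaluator Global Assessment through 39 weeks post treatment", against the endpoint list, "The change from baseline in the Evaluator Global Assessment at 39 weeks post treatment", is editorial and does not change this.

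A second objection is that secondary tests are conventionally read only after a successful primary. That may be the intent, but a convention is not a rule in the plan, and the hierarchy sentence is confined to the secondaries.

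A third is that the rescue fault is an obvious slip, last in the order, and that a contrast in a three-group section implies the one-way ANOVA described for other endpoints. Both observations are fair. The slip affects no earlier test, but it sits in a formal hypothesis in both documents and the model is left to inference.

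**Conclusion.** The gap between the primary test and the secondary hierarchy is real and should be closed before unblinding. With an ungated sequence, familywise error for Cingal versus TH is 9.75% under independence (8.9% to 9.3% allowing for the conservatism of Fisher's test at the planned group sizes), 7.8% at correlation 0.8 and 7.0% at 0.9. The correlations are assumptions, and the figures take all nulls as true and the sequence as stopping at its first failure. Gating on the primary brings the rate to 5%.

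The primary claim is at or below 5% under every reading; the excess concerns secondary claims only. The PGA/EGA sentences and the rescue null are wording clarifications of lower weight. The 14.3% and 18.5% figures should not be cited as consequences of the plan: the wording permits those readings but does not favour them.

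**What to change.** In Protocol 12.1.2 and SAP 4.1.3:

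1. State that testing runs from the primary endpoint to the seven secondary endpoints in the listed order, Cingal versus TH at week 39 (rescue use: through week 39), each at two-sided 5%; that it stops at the first p>0.05; and that later p-values are descriptive.
2. Limit the two no-adjustment sentences to visits other than week 39, and call those analyses exploratory, in line with SAP 3.3 and 4.1.4.
3. Define both rescue parameters as mean total rescue use through week 39, in Cingal and in TH, tested by the Cingal-versus-TH contrast from the three-group one-way ANOVA without a baseline covariate.

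This keeps the sponsor's endpoints, order and 5% level, and needs no new data and no change in sample size. The cost is in claims: secondary p-values after the first failure become descriptive, and all seven do if the primary fails.

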9 ELIGIBILITY

9.1 Enrollment Criteria

9.1.1 Inclusion Criteria

1. Only subjects that were enrolled and met the inclusion criteria for the Cingal 16-02 trial and signed the informed consent are eligible for Cingal 17-02.
2. Subject is able to understand and comply with the requirements of Cingal 17-02 and voluntarily provides consent.

Patients will not be rescreened at enrollment to Cingal 17-02 as these patients were enrolled and met the inclusion / exclusion criteria for the Cingal 16-02 clinical trial. All patients enrolled in the Cingal 16-02 trial will be eligible to participate in Cingal 17-02.

For reference only, the inclusion criteria used in Cingal 16-02 were:

1. Subject is 40-75 years old, with a Body Mass Index (BMI) $\leq 40 \text{ kg/m}^2$.
2. Subject has Kellgren-Lawrence (K-L) severity grade I, II or III in the index knee as determined by X-ray. Contralateral knee: K-L severity grade 0, I or II.
3. Subject has had at least two signs and at least two symptoms of OA disease (based on the European League Against Rheumatism (EULAR) recommendations for diagnosing knee OA in the index knee for at least 6 months despite conservative treatment (weight reduction, physical therapy, pain medications, etc.). The EULAR signs and symptoms are as follows:
 - a. Signs: crepitus, restricted movement and bony enlargement
 - b. Symptoms: persistent knee pain, limited morning stiffness and reduced function

4. Subject must be willing to abstain from other intraarticular (IA) treatments of the knee for the duration of the study.
5. Subject is willing to discontinue all analgesics including NSAIDs, except acetaminophen/paracetamol, at least seven days before the treatment injection and through the completion of the study.
6. Subject is willing to use only acetaminophen/paracetamol (up to a maximum of 4.0 grams per day per the package insert) for the treatment of joint pain for the duration of the study. At least forty eight hours prior to the Baseline Visit and each follow-up visit, the subject is willing to discontinue use of acetaminophen/paracetamol.
7. Subject is willing to maintain a stable dose of oral glucosamine and/or chondroitin sulfate products throughout the study, if taken prior to signing the informed consent form (ICF).
8. Subject is able to understand and comply with the requirements of the study and voluntarily provides consent.

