10 STUDY PROCEDURES

10.1 Schedule of Events

	Pre-Treatment	Treatment		Post-Treatment Follow-Up Visits						17-02 Follow-Up Visits	
		Day 0 (7-14 days after screening visit)		1 week	3 weeks	6 weeks	12 weeks	18 weeks	26 weeks	Consent	39 Weeks
Assessments	-7 to -14 Days	Day 0 (7-14 days after screening visit)		1 week	3 weeks	6 weeks	12 weeks	18 weeks	26 weeks	Consent	39 Weeks
	Screening	Baseline	Treatment	±3 days			± 1 week				
Informed Consent	X									X	
Demographics Medical History	X										
Physical Exam, Vitals, BMI	X										
Urine / Blood Pregnancy Test	X										
Chemistry/Hematology/Urinalysis	X										
Bilateral Knee X-rays and assessment of K-L	X										
Review of X-rays by Independent Radiologist	X										
Physical Evaluation (Both Knees)	X	X		X	X	X	X	X	X		X
ROM (Index Knee)	X	X		X	X	X	X	X	X		X
ROM (Contralateral Knee)	X	X					X		X		X
WOMAC (Both Knees)	X	X		X	X	X	X	X	X		X
Evaluation of Enrollment Criteria	X	X	X							X	
Stop Analgesics/NSAIDs except Paracetamol	X										
Assess D/C Paracetamol ≥ 48 hours before Visit		X		X	X	X	X	X	X	X	X
Paracetamol Dispense/Pill Count	X	X		X	X	X	X	X	X	X	X
Distribute Subject Diary	X										X
Randomization			X								
Aspiration/ Evaluation of Synovial Fluid			X								
IA Injection			X								
Evaluate Diary		X		X	X	X	X	X	X		X
EuroQol		X		X	X	X	X	X	X		X
Patient Global Assessment		X		X	X	X	X	X	X		X
Evaluator Global Assessment		X		X	X	X	X	X	X		X
Concomitant Medication Assessment				Throughout the study							
Adverse Event Assessment				Throughout the study							

† -Cells in grey indicate assessments conducted only during Cingal 16-02 trial.

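### Rescue-medication use is the only one of the seven hierarchical secondary endpoints with no named baseline covariate (and no named model), although run-in paracetamol use is recorded before injection; the cost is some precision, of unknown size

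*SAP*

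**What the plan says.** SAP 4.1.3 lists seven secondary endpoints and says of them: "In order to preserve the integrity of the Type I error, these will be tested in a hierarchical manner". The order of testing is the order of presentation, and rescue medication comes last.

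The first six each carry a named baseline covariate:

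- WOMAC Pain: "Data will be analyzed via an analysis of variance (ANOVA) with a term for treatment and baseline pain score as a covariate".
- WOMAC Physical Function: "baseline Physical Function score as a covariate".
- WOMAC Stiffness: "baseline Stiffness score as a covariate".
- Total WOMAC: its own baseline score.
- Patient and Evaluator Global Assessments: their own baseline scores in the SAP. Protocol 12.1.2 uses baseline pain for both.

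For the seventh the text is "This secondary efficacy endpoint is the usage of rescue medications through 39 weeks post treatment comparing the Cingal group to the TH group", followed only by a statement that a predefined Cingal–TH contrast will be used. No model, response scale or covariate is given. The hypothesis defines the Cingal term as total rescue use and the TH term as mean change in WOMAC Pain. Protocol 12.1.2 repeats this.

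On what is recorded before injection, Protocol 10.1 has a row "Paracetamol Dispense/Pill Count" marked at Screening and at Baseline, and a diary evaluation at Baseline. Baseline falls 7 to 14 days after Screening. Paracetamol is the only analgesic allowed in the week before injection (Protocol 9.1.1, quoted up to its last word: "Subject is willing to discontinue all analgesics including NSAIDs, except acetaminophen/paracetamol, at least seven days before the treatment injection and through the completion of the"). Protocol section 2 also requires rescue medication to stop at least 48 hours before Baseline. Protocol 10.2.1 carries all Cingal 16-02 data into Cingal 17-02.

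**The concern.** People differ in how many tablets they take for the same pain. If some of that difference persists from run-in to follow-up, a comparison of post-injection use that ignores run-in use leaves explainable variation in the error term. The plan makes this kind of adjustment for the other six secondaries, and the data for it are already collected here.

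The TH arm has only 64 subjects, so it sets the precision of the Cingal–TH contrast. At stake is a somewhat wider interval and somewhat lower power for one formally tested secondary. A further risk is that a covariate chosen later, under the additional-analyses clause, would not be prespecified.

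**Working it through.** **1. Is the covariate supplied elsewhere?** No. SAP 4.6 keeps to the covariates already specified and brings in further factors only through later stepwise analyses. Protocol 12.6 says the analyses run without covariates, which disagrees both with SAP 4.6 and with Protocol 12.1.2. SAP 4.2 defines baseline for computing changes, and rescue use is not described as a change.

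**2. What does the run-in measure?** The run-in lasts 7 to 14 days. Removing at least 2 days of washout leaves at most 7 − 2 = 5 to 14 − 2 = 12 days of possible use. The Screening mark most naturally means dispensing; the usable count is the one at Baseline, with the diary as a second source.

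**3. Reproduce the plan's own figure.** The only power calculation for Cingal v TH is for WOMAC Pain at 26 weeks: 10 mm, SD 20, two-sided 5%, 90% power, 2:1 (Protocol 12.1, SAP 4.1.1). The t-test calculation gives 63.7, so 64 TH and 128 Cingal, as stated. Power at 128 v 64 is 90.1%. The documents give no SD, effect or power for rescue use.

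**4. Precision at the planned arms of 256 v 64.** In units of the outcome SD:

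SE = √(1/64 + 1/256) = √0.01953 = 0.140

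Difference detectable with 80% power (normal approximation) = (1.960 + 0.842) × 0.1398 = 0.392 SD

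**5. Effect of the covariate.** With correlation ρ between run-in and post-injection use, residual variance is multiplied by 1 − ρ². Power is two-sample noncentral t, two-sided 5%, with standardised difference d/√(1 − ρ²). Both ρ and d are assumptions. d = 0.5 is 10/20, borrowed from the pain calculation; d = 0.35 is a smaller illustrative value.

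| ρ | Variance factor | Detectable at 80% power (SD) | Power, d = 0.5 | Power, d = 0.35 |
|---|---|---|---|---|
| 0 | 1.00 | 0.392 | 94.6% | 70.4% |
| 0.2 | 0.96 | 0.384 | 95.4% | 72.2% |
| 0.3 | 0.91 | 0.373 | 96.2% | 74.5% |
| 0.5 | 0.75 | 0.339 | 98.5% | 82.2% |

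The gains over no covariate are 0.8, 1.6 and 3.9 points at d = 0.5, and 1.8, 4.1 and 11.8 points at d = 0.35. At ρ = 0.1 the variance factor is 0.99 and the gain is negligible.

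These figures assume all 256 and 64 subjects contribute and that a t-type comparison suits the outcome. Skewed pill counts may need a different model, so the table illustrates and does not predict.

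**The case against.** The strongest reply is that there is no unadjusted analysis to improve. The paragraph gives a contrast without a model, and a hypothesis whose two terms measure different things. That defect is more basic and has to be repaired first. This stands, and it shapes the fix: the covariate belongs in the same edit. A reader might infer that the plan deliberately chose an unadjusted model; the text does not go that far.

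Second, the covariate may be weak. At most about 5 to 12 days of use, just after other analgesics are withdrawn, need not represent habitual use or predict use over 39 weeks. The documents offer no evidence on this. That also stands, and it is why the low-ρ rows matter as much as the ρ = 0.5 row.

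Third, a reader might infer that chance imbalance in analgesic habit biases an unadjusted comparison. It does not: under randomisation such imbalance is already reflected in the standard error. With an SE of 0.140 SD, a chance difference in mean run-in use of up to about 1.96 × 0.140 = 0.27 SD would be unremarkable. Adjustment reduces that noise; it does not correct an invalid test.

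Fourth, the other six endpoints are changes from baseline and this one is a post-treatment total, so the difference in treatment is not in itself an inconsistency. The primary Fisher's exact test is unadjusted too. This is fair: the case rests on efficiency, not on uniformity.

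Finally, the endpoint is seventh in the order, so it is tested confirmatorily only if the six secondaries before it succeed. The powers above are not the chance of reaching and winning that test.

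**Conclusion.** The point holds as a modest improvement. Rescue use is the only hierarchical secondary with no named baseline covariate; a pre-injection measure is scheduled, its data carry over, and no other section supplies the adjustment.

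The benefit is precision only, and its size cannot be settled from the documents. At the planned 256 v 64 with d = 0.5 it is about 1 to 2 points of power for ρ of 0.2 to 0.3. A reader might take the gain of about 12 points as the expected benefit. It needs both ρ = 0.5 and d = 0.35, neither of which the documents support. The conclusion that adjustment helps assumes only that run-in and later use are positively correlated. If they are nearly uncorrelated, the covariate costs about one degree of freedom and gains nothing.

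**What to change.** Rewrite the rescue-medication paragraph once, in SAP 4.1.3 and Protocol 12.1.2, before unblinding:

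- Define the response identically in both arms, as rescue tablets per day from injection to week 39, and correct the hypothesis to match.
- Name the model, for example ANCOVA on a transformed rate, or a count model with an offset for days observed, since pill counts may be skewed.
- Prespecify run-in tablets per day from Screening to Baseline as a covariate, stating whether the pill count or the diary is the source and how the washout days enter the denominator. Baseline WOMAC Pain is an optional second covariate; the figures above do not cover it.
- Keep the unadjusted Cingal–TH contrast as a sensitivity analysis.
- Reconcile Protocol 12.6 with SAP 4.6 on whether analyses carry covariates.

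No new data are needed. The cost is more than a single line, because the response and model must be written as well, but that work is required whether or not a covariate is added; the covariate itself is one further term. The downside is a noisy covariate, so the gain may be small.
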